## **10.4 Appendix 4: Contraceptive guidance and collection of pregnancy information**

### **Definitions**

#### **Woman of Childbearing Potential (WOCBP)**

A woman is considered fertile following menarche and until becoming post-menopausal unless permanently sterile (see below).

Women in the following categories **are not considered WOCBP**:

1. Premenarchal
2. Premenopausal female with 1 of the following:
  - Documented hysterectomy
  - Documented bilateral salpingectomy
  - Documented bilateral oophorectomy
3. Postmenopausal female
  - A postmenopausal state is defined as no menses for 12 months without an alternative medical cause. A high follicle stimulating hormone level in the postmenopausal range may be used to confirm a postmenopausal state in women not using hormonal contraception or hormonal replacement therapy (HRT). However, in the absence of 12 months of amenorrhea, a single follicle stimulating hormone measurement is insufficient.
  - Females on HRT and whose menopausal status is in doubt will be required to use one of the non-estrogen hormonal highly effective contraception methods if they wish to continue their HRT during the study. Otherwise, they must discontinue HRT to allow confirmation of postmenopausal status before study enrollment.

### **Contraception Guidance**

Female participants of childbearing potential are eligible to participate if they agree to use a highly effective method of contraception consistently and correctly as described in the table below.

## Highly Effective Contraceptive Methodsa

### Highly Effective Contraceptive Methods That Are User Dependentb

Failure rate of <1% per year when used consistently and correctly.

Combined (estrogen and progestogen containing) hormonal contraception associated with inhibition of ovulation

- Oral
- Intravaginal
- Transdermal

Progestogen only hormonal contraception associated with inhibition of ovulation

- Oral
- Injectable

### Highly Effective Methods That Are User Independent

Implantable progestogen only hormonal contraception associated with inhibition of ovulation

- Intrauterine device
- Intrauterine hormone-releasing system
- Bilateral tubal occlusion

### Vasectomized partner

A vasectomized partner is a highly effective contraception method provided that the partner is the sole male sexual partner of the WOCBP and the absence of sperm has been confirmed. If not, an additional highly effective method of contraception should be used.

### Sexual abstinence

Sexual abstinence is considered a highly effective method only if defined as refraining from heterosexual intercourse during the entire period of risk associated with the IMP. The reliability of sexual abstinence needs to be evaluated in relation to the duration of the study and the preferred and usual lifestyle of the participant.

### NOTES:

- a) In case of newly started contraception pills/intrauterine devices, Investigator should consider the correct timing of starting/applying such methods in relation to the menstrual cycle and the manufacturing instruction as when these newly started methods would become effective.
- b) Typical use failure rates may differ from those when used consistently and correctly. Use should be consistent with local regulations regarding the use of contraceptive methods for participants participating in clinical studies.

### Pregnancy testing

- WOCBP should only be included after a confirmed menstrual period and a negative highly sensitive serum pregnancy test.
- Additional pregnancy testing should be performed as indicated in the Schedule of Activities (Table 1-1) during the treatment period and at 20 weeks after the last dose of IMP and as required locally.
- Pregnancy testing will be performed whenever a menstrual cycle is missed or when pregnancy is otherwise suspected

## Male participants with partners who become pregnant

- The Investigator will attempt to collect pregnancy information on any male participant's female partner who becomes pregnant while the male participant is in this study. This applies only to male participants who receive IMP. If the study participant is later found to be on placebo, then pregnancy data collection can stop.
- In cases where the partner of a male subject enrolled in a clinical study becomes pregnant, the Investigator or designee is asked to contact the subject to request consent of the partner via the Partner Pregnancy Consent form that has been approved by the responsible IRB/IEC and should be available in the Investigator site file. In case of questions about the consent process, the Investigator may contact the UCB/CRO contract monitor for the study. The Investigator will complete the information in the eCRF only after the partner has agreed that additional information can be captured and has provided the signed Partner Pregnancy Consent form. UCB's Patient Safety department is also the primary contact for any questions related to the data collection for the partner pregnancy, eventual birth, and follow up.
- After obtaining the necessary signed informed consent from the pregnant female partner directly, the Investigator will record pregnancy information on the appropriate form and submit it to the Sponsor within 1 working day of learning of the partner's pregnancy. The female partner will also be followed to determine the outcome of the pregnancy. Information on the status of the mother and child will be forwarded to the Sponsor. Generally, the follow-up will be at least 12 months after the delivery date. Any termination of the pregnancy will be reported regardless of fetal status (presence or absence of anomalies) or indication for the procedure.

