#### **4.1.2 Initial Treatment Period (Weeks 0-16) and Maintenance Treatment Period (Weeks 16-48)**

Eligible study participants will be randomized in a 2:2:2:1 ratio as noted in the Study Schema to:

- Bimekizumab 320mg Q2W from Weeks 0 to 48
- Bimekizumab 320mg Q4W from Weeks 0 to 48
- Bimekizumab 320mg Q2W to Week 16, continuing on 320mg Q4W from Weeks 16 to 48
- Placebo to Week 16, continuing on bimekizumab 320mg Q2W from Weeks 16 to 48

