The Maintenance Treatment Period is designed to assess the durability of response of the study endpoints and to provide sufficient longer-term (up to 48 weeks, including the Initial Treatment Period) safety and exposure to bimekizumab for regulatory filings. Continuous (up to 48 weeks) exposure to both the 320mg bimekizumab Q2W and 320mg bimekizumab Q4W dose regimens allow for the following assessments:

- Durability of response and longer-term safety
- Optimal dosing interval for maintenance treatment

This period will also allow study participants who received placebo in the Initial Treatment Period to begin receiving bimekizumab at Week 16 in the randomized, controlled Maintenance Treatment Period of the study.

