#### **Prior/Concurrent clinical study experience**

25. Study participant has previously participated in this study or study participant has previously been assigned to treatment in a study of the medication under investigation in this study, and received at least 1 dose of IMP (including placebo).

26. Study participant is currently participating in another study of a systemic medication under investigation, including SFU. Study participant must be washed out of the medication as indicated in [Table 6-3](#).

27. Study participant is currently participating in another study of a topical medication under investigation, including SFU. Study participant must be washed out of the medication for 4 weeks prior to the Baseline Visit.

28. Study participant is currently, or was within the 4 weeks prior to the Baseline Visit, participating in another study of a medical device under investigation.

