### **8.3.5 Pregnancy**

Details of all pregnancies in female participants and female partners of male participants who become pregnant will be collected after the start of study treatment and through the SFU visit (ie, 20 weeks after last dose of IMP).

If a pregnancy is reported, the Investigator must immediately inform the Sponsor within 24 hours of learning of the pregnancy and should follow the procedures outlined in Appendix 4.

A female study participant should be withdrawn from the study as soon as pregnancy is known (by positive pregnancy test), and the following should be completed:

- The study participant should return for an early discontinuation visit.
- The study participant should immediately stop the intake of the IMP.
- An SFU Visit should be scheduled 20 weeks after the study participant has received her last dose of IMP.

Abnormal pregnancy outcomes (eg, spontaneous abortion, fetal death, stillbirth, congenital anomalies, ectopic pregnancy) are considered SAEs.

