## **9.8       Determination of sample size**

A total of 490 study participants will be randomly assigned in a 2:2:2:1 ratio to the following treatment arms:

- Bimekizumab 320mg Q2W during Initial Treatment Period (Weeks 0-16) and Maintenance Treatment (Weeks 16-48) Periods, N=140
- Bimekizumab 320mg Q2W during Initial Treatment Period (Weeks 0-16), and Bimekizumab 320mg Q4W during Maintenance Treatment Period (Weeks 16-48), N=140
- Bimekizumab 320mg Q4W during Initial Treatment (Weeks 0-16) and Maintenance Treatment Periods (Weeks 16-48), N=140
- Placebo during Initial Treatment Period (Weeks 0-16), and Bimekizumab 320mg Q2W during Maintenance Treatment Period (Weeks 16-48), N=70

The analysis of the primary efficacy endpoint and secondary efficacy endpoints are based on a comparison of bimekizumab versus placebo at Week 16, with alpha adjustment strategy as indicated in Section 9.3.1 and Section 9.3.2.

The power to detect a statistically significant difference for each of the endpoints are shown in Table 9-1. Notably, with a 2-sided significance level of 0.025, the sample size of 140:70

provides 73% power for detecting at least a difference of 1.5 (bimekizumab Q4W vs placebo) for the Worst Pain change from Baseline (CFB) endpoint.

Given the high level of power for each of the primary and key secondary endpoints at the 0.025 significance level for the Q2W comparison (power $\geq$ 0.89), and per the alpha spending strategy, there is a high likelihood that the Q4W comparison of Worst Pain CFB vs placebo will be allowed to be tested against the 0.05 level of significance. The power for this latter test is 81%. The sample size is thus ultimately driven by the Worst CFB endpoint. Furthermore, the randomization ratio of 2:2:2:1 has been chosen to provide study participants with a high probability (6/7 ~ 86%) of being randomized to active study drug.

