## Female Participants who become pregnant

- Any female participant who becomes pregnant while participating in the study will discontinue IMP or be withdrawn from the study.
- The Investigator will collect pregnancy information on any female participant who becomes pregnant while participating in this study. Information will be recorded on the appropriate form and submitted to the Sponsor within 1 working day of learning of a participant's pregnancy. The participant will be followed to determine the outcome of the pregnancy. The Investigator will collect follow-up information on the participant and the neonate and the information will be forwarded to the Sponsor. Generally, the follow-up will be at least 12 months after the delivery date. Any termination of pregnancy will be reported, regardless of fetal status (presence or absence of anomalies) or indication for the procedure.
- While pregnancy itself is not considered to be an AE or SAE, any pregnancy complication or elective termination of a pregnancy will be reported as an AE or SAE. A spontaneous abortion is always considered to be an SAE and will be reported as such. Any post-study pregnancy related SAE considered reasonably related to the IMP by the Investigator will be reported to the Sponsor as described in Section 8.3.5. While the Investigator is not obligated to actively seek this information in former study participants, he or she may learn of an SAE through spontaneous reporting.

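### Appendix 4 lets partner-pregnancy follow-up stop for a man found to be on placebo without reference to bimekizumab exposure, and it gives a different pregnancy reporting limit from Section 8.3.5

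*Protocol*

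**What the plan says.** **Stop rule.** Appendix 4, under male participants with partners who become pregnant, first sets the scope: "This applies only to male participants who receive IMP". It then adds: "If the study participant is later found to be on placebo, then pregnancy data collection can stop". The same section says that follow-up generally lasts at least 12 months after delivery.

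**Treatment of the placebo arm.** Section 4.1.2 describes it as "Placebo to Week 16, continuing on bimekizumab 320mg Q2W from Weeks 16 to 48". Section 4.2 gives the purpose of the Maintenance Treatment Period: "This period will also allow study participants who received placebo in the Initial Treatment Period to begin receiving bimekizumab at Week 16". Section 9.8 lists the arm as "Placebo during Initial Treatment Period (Weeks 0-16), and Bimekizumab 320mg Q2W during Maintenance Treatment Period (Weeks 16-48), N=70".

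**General collection rule.** Section 8.3.5 covers all pregnancies in female participants and in partners of male participants, from the start of study treatment through the safety follow-up (SFU) visit. It makes no exception for placebo and sends the site to Appendix 4 for procedures.

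**Reporting limits.** Section 8.3.5 states that "the Investigator must immediately inform the Sponsor within 24 hours of learning of the pregnancy". For female participants, Appendix 4 has the information recorded on a form and "submitted to the Sponsor within 1 working day of learning of a participant's pregnancy". For partners it also sets 1 working day from learning of the pregnancy, with the form completed once the partner has signed consent.

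**The concern.** The stop rule is worded for a trial in which a placebo participant never receives the drug. Here the placebo label describes only the first 16 weeks. A man identified as belonging to the placebo arm may have been on bimekizumab when his partner conceived, or may have started it during her pregnancy. If a site applies the sentence by randomized arm, it has written permission to end follow-up of the pregnancy and the infant. Any such loss would fall in one arm only and would concern exposed cases that Section 8.3.5 intends to collect.

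The second issue is that a site reading Section 8.3.5 and then Appendix 4, as it is told to, finds two time limits for the same trigger. A pregnancy learned of before a weekend can be on time under one and late under the other. What is at stake is the completeness and timeliness of a small part of the safety record.

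**Working it through.** The protocol gives no figure on this point to reproduce. The check sets the sections side by side and adds simple arithmetic on the size of the arm and the time involved.

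**1. Is there a placebo-only arm?** No. Sections 4.1.2, 4.2 and 9.8 agree that the placebo arm moves to bimekizumab at Week 16.

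- Share of the trial: 70/490 = 14.3%.
- Treatment weeks on bimekizumab by design: (48 − 16)/48 = 32/48 = 66.7%.
- Dosing visits at Weeks 16 to 46, every 2 weeks: (46 − 16)/2 + 1 = 16.
- For those who do not enter HS0005, the SFU visit falls at Week 46 + 20 = Week 66. Adding 2 to 5 weeks of screening gives 68 to 71 weeks, which matches the Synopsis. Time on or after bimekizumab is then (66 − 16)/66 = 50/66 = 75.8%.

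The 75.8% applies only to participants who do not enter HS0005. For those who enter at Week 48, the figure is 66.7%.

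**2. What does the rule permit in each case?**

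| Man randomized to placebo | Bimekizumab exposure | Rule read by randomized arm | Rule read by treatment at conception |
|---|---|---|---|
| Stops before Week 16 | None | Stop allowed | Stop allowed |
| Partner conceives before Week 16, man continues past Week 16 | None before conception, some during the pregnancy | Stop allowed | Stop allowed |
| Partner conceives after his Week 16 dose | Before conception | Stop allowed | Stop not allowed |

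The readings part company in the third row, and the text does not say which is meant. In the second row both readings allow a stop although the man is dosed during the pregnancy. The protocol does not say whether that exposure counts.

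**3. When would a man be found to be on placebo?** An emergency code break (Section 6.3.2.2) returns treatment arm and dose. The scheduled unblinded analysis (Section 9.7.2) comes only after the last participant has completed Week 48 or discontinued before it. By then every placebo-randomized man who took his Week 16 dose has received bimekizumab. With follow-up generally running at least 12 months after delivery, allocation may become known while follow-up is still open.

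**4. Does the scope sentence resolve it?** No. It limits collection to men who receive IMP, but Table 6-1 classes placebo as IMP, and exclusion criterion 25 counts placebo as a dose of IMP. The sentence therefore does not separate exposed from unexposed men.

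**5. How many men?** The protocol does not state the sex split, so the number lies somewhere between 0 and 70. As an illustration only, the 3:1 female-to-male ratio in Section 2.2, a European population figure and not a trial enrolment figure, would give 70 × 0.25 = 17.5, about 18 men. This counts men, not pregnancies. No expected number of pregnancies is given.

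**6. The two limits.** Both run from learning of the pregnancy. Midweek, 24 hours and 1 working day can coincide. For a pregnancy learned of on a Friday, and assuming a Saturday-Sunday weekend, 24 hours ends on Saturday and 1 working day ends on Monday, at about 72 hours. The gap is about 72 − 24 = 48 hours, and longer over a public holiday.

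**The case against.** The strongest defence is that the rule speaks of being on placebo, not of being randomized to it. From Week 16 nobody is on placebo, and a code break that shows arm and dose should make this plain. On that reading a man whose partner conceives while he is on bimekizumab falls outside the rule. The rule is also permissive, and it can be taken as a procedural detail beneath the general duty in Section 8.3.5. These are fair readings, but the protocol states none of them. Table 6-1 names an arm simply as placebo, so reading the phrase as the arm label is equally natural.

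On timing, 24 hours could be the first notice and 1 working day the completed form. The SAE paper-CRF instructions in Appendix 3 make a similar split between telephone notice and the form. The protocol does not make it for pregnancy. It remains true that a site observing Section 8.3.5 would inform the Sponsor within 24 hours whatever Appendix 4 says.

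A reader might infer more than the documents support:

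- That every placebo participant receives bimekizumab. Those who stop before Week 16 do not, and for them the rule is sound.
- That exposed pregnancies will be lost or reported late. The wording makes this possible, not certain.
- That pregnancies of female participants are affected by the stop rule. Appendix 4 contains no placebo stop for them.
- That the reporting limits always conflict. They differ only around weekends and holidays.

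**Conclusion.** The point holds in limited form. The stop rule is keyed to a label that does not identify exposure in this design. Read by randomized arm, it could permit follow-up of a bimekizumab-exposed partner pregnancy to end, and Section 8.3.5 provides no such exception. The rule fits only men with no bimekizumab exposure. The reporting limits in Section 8.3.5 and Appendix 4 are not equivalent and are not distinguished by purpose.

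The consequence is small. One arm of 70 is involved, with an unstated number of men and, in all likelihood, few pregnancies. The conclusion rests on the wording and on the planned switch at Week 16. It does not depend on the assumed share of men. The primary estimand, the sample size and the efficacy conclusions are untouched. It is worth correcting because it concerns safety data and the correction is cheap.

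**What to change.** 1. In Appendix 4, replace the condition of being found on placebo with one based on actual exposure: partner-pregnancy data collection may end early only if the man is confirmed to have received no bimekizumab in the relevant period. The sponsor should define that period and say whether a first bimekizumab dose after conception counts.
2. Align this with Section 8.3.5, either by stating the exception there or by having Appendix 4 refer back to the general rule. Clarify in the same place whether the restriction to men who receive IMP is meant to include placebo.
3. Reconcile the reporting limits in Section 8.3.5 and both parts of Appendix 4. Either use one limit throughout, or say which applies to first notification and which to the completed form. For partners, also say how the limit for the form runs while signed consent is awaited.

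The cost is a few sentences in Section 8.3.5 and Appendix 4 and probably no more than a handful of additional follow-ups. No assessment, dosing rule or analysis changes.

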## Female Participants who become pregnant

- Any female participant who becomes pregnant while participating in the study will discontinue IMP or be withdrawn from the study.
- The Investigator will collect pregnancy information on any female participant who becomes pregnant while participating in this study. Information will be recorded on the appropriate form and submitted to the Sponsor within 1 working day of learning of a participant's pregnancy. The participant will be followed to determine the outcome of the pregnancy. The Investigator will collect follow-up information on the participant and the neonate and the information will be forwarded to the Sponsor. Generally, the follow-up will be at least 12 months after the delivery date. Any termination of pregnancy will be reported, regardless of fetal status (presence or absence of anomalies) or indication for the procedure.
- While pregnancy itself is not considered to be an AE or SAE, any pregnancy complication or elective termination of a pregnancy will be reported as an AE or SAE. A spontaneous abortion is always considered to be an SAE and will be reported as such. Any post-study pregnancy related SAE considered reasonably related to the IMP by the Investigator will be reported to the Sponsor as described in Section 8.3.5. While the Investigator is not obligated to actively seek this information in former study participants, he or she may learn of an SAE through spontaneous reporting.

## **10.5 Appendix 5: Genetics**

### **Use and Analysis of DNA**

Samples for potential future exploratory biomarker research will be collected and stored from consenting participants in the study. This sampling is optional for study participants and requires a separate informed consent. A decision not to consent does not exclude the study participant from the study:

- Blood sample for DNA.

These samples will only be used to further understanding of HS and/or how biomarkers, including genetic variation, may affect response or be affected by treatment with bimekizumab, background products, and/or concomitant medications in study participants with HS.

This document cannot be used to support any marketing application and any extensions or variations thereof.  
PUBLIC COPY

---

## **10.6 Appendix 6: Liver safety – suggested actions and follow-up assessments**

Participants with potential drug-induced liver injury must be assessed to determine if IMP must be discontinued, as outlined in Section 7.1.2.

All PDILI events must be reported as an AE, and PDILI events meeting SAE criteria should be reported to the Sponsor within 24 hours of learning of the occurrence. Any PDILI event that meets the criterion for potential Hy's Law must be reported within 24 hours of learning of the occurrence as an AE of special interest (Section 8.3.6), and, if applicable, also reported as an SAE (Section 8.3).

Evaluation of PDILI consists of the diagnostic testing and continued monitoring included in Table 10-1 (specific tests dependent on laboratory results and corresponding symptoms) and consultation with a local hepatologist (if applicable; discussed in Section 10.6.1). The local hepatologist is the expert usually consulted by the treating physician for assessment and management of potential hepatic disease. This would usually be a hepatologist, but may be a gastroenterologist. Additional investigation and monitoring may be required and adapted based on the diagnosis after the cause of the liver injury/abnormality is confirmed (details in Section 7.1.2.1.1).

This document cannot be used to support any application and any extensions or variations of authorization  
PUBLIC COPY

